8.8.2. Reporting of Adverse Events

For all adverse events occurring during the study period, data must be entered in the Adverse Event eCRF in the EDC system. For serious adverse events (SAEs), the section of the eCRF describing the serious nature of the AE must also be completed.

All device and procedure related adverse events will be investigated by Endologix.

The PI should supply to Endologix and the responsible EC/IRB with a complete, written case history (AE forms) and any additional redacted source documentation and information (e.g., other diagnostic testing, discharge reports, autopsy reports, etc.) as it is available.

Deaths

For any death, regardless of cause or timing, it is recommended that the site notify the Endologix Clinical Department via the EDC system within 1 working day of awareness. The PI should supply to Endologix and the responsible EC/IRB with a complete, written case history (AE forms) and any additional redacted source documentation and information (e.g., other diagnostic testing, discharge reports, autopsy reports, etc.).

In all cases, the death certificate is to be uploaded to the EDC system. Every attempt should be made to obtain as much detailed information on the events or conditions leading up to the death as possible. If the patient was hospitalized, a copy of the discharge summary source document is required. Also sites can search Social Security Death Index (SSDI) or CDC National Death Index (NDI) to obtain more information.

If approval is obtained from the patient or a patient's authorized family member, the site should notify Endologix for submission of the explant to Endologix. A device explant kit will be provided to the hospital for processing and shipment to an independent pathologist per established methods. To request a kit, send a fax to Endologix at [contact], or contact Endologix by telephone at [contact].

8.8.3. Adverse Events: required reporting timeframes

Note: Site reporting times to Endologix only; responsible IRB/EC reporting requirements must still be followed by the site, in addition to those recommended below.

AE Type	Reporting Recommendations
Non-device or procedure related AE	Recommended monthly at minimum
Device or procedure related AE	Within 10 working days
Non-device or procedure related SAE	Within 10 working days
Device or Procedure related SAE	Within 1 working day
Death as outcome (regardless of cause)	Within 1 working day
Unanticipated Adverse Device Effect	Within 1 working day

8.8.4. Secondary procedures

For subjects that experience any non-diagnostic invasive secondary treatment of the groin access

Confidential. This document and the information contained herein may not be reproduced, used or disclosed without written permission from Endologix, Inc.

areas or of the abdominal aortoiliac vessels (e.g., hematoma drainage, vascular exploration for bleeding, iliac stenting, thrombectomy, additional device placement for endoleak, embolization for Type II endoleak, conversion to open repair, etc.), it is important to identify the specific procedure performed on the relevant **ADVERSE EVENT** eCRF. A copy of the discharge summary source document should be uploaded to the EDC system.

8.8.5. Anticipated Adverse Events

Adverse events that could potentially occur during this investigation are called anticipated adverse events. These events must be reported if clinically significant. A list of anticipated AEs are listed in alphabetical order:

- Access site complications and sequelae (e.g., dehiscence, infection, pain, hematoma, pseudoaneurysm)
- Allergic reaction to contrast agent (e.g., pruritus, urticaria, bronchospasm, angioedema, hypotension or anaphylaxis that occurs during or post-procedure)
- Amputation
- Anesthetic complications and sequelae (e.g., aspiration)
- Aneurysm enlargement
- Aneurysm rupture
- Arterial damage or trauma (e.g., bleeding, perforation, dissection, rupture)
- Arterial or venous thrombosis and/or pseudoaneurysm
- Arteriovenous fistula
- Bleeding requiring transfusion and/or surgical intervention
- Bowel complications (e.g., ileus, ischemia, infarction, necrosis)
- Cardiac complications and sequelae (e.g., arrhythmia, myocardial infarction, congestive heart failure, hypotension, hypertension)
- Catheter or implant component fragmentation and sequelae (e.g., embolization, vessel trauma)
- Claudication
- Coagulopathy
- Death (due to any cause)
- Edema
- Embolization (micro and macro) with transient or permanent ischemia or infarction
- Endoleak
- Fever and localized inflammation
- Genitourinary complications and sequelae (e.g., ischemia, fistula, incontinence, hematuria, impotence, infection)
- Hepatic failure
- Infection of the aneurysm, device access site, including abscess formation, transient fever and pain.
- Local or systemic neurologic complications and sequelae, transient or permanent (e.g., stroke, transient ischemic attack, paraplegia, paraparesis, paralysis, numbness and/or tingling in legs)
- Lymphatic complications and sequelae (e.g., lymph fistula)
- Nellix implant: improper component placement; incomplete component deployment; component migration; occlusion/thrombosis; infection; stent fracture; EndoBag material wear; dilatation; erosion; puncture and perigraft flow

- Thrombosis or occlusion of stent graft or arterial vessel of the lower extremities
- Pulmonary/respiratory complications and sequelae (e.g., pneumonia, respiratory failure, prolonged intubation, pulmonary embolism)
- Renal complications and sequelae (e.g., artery occlusion, infarction, insufficiency, failure)
- Secondary Intervention
- Surgical conversion to open repair

8.8.6. Unanticipated Adverse Device Effect

The investigator shall submit to Endologix and to the reviewing EC/IRB a report of any unanticipated adverse device effect occurring during an investigation as soon as possible, but in no event later than 24 hours after the PI first learns of the effect. PIs must submit to Endologix documentation of the report made to the EC/IRB via the EDC system. Endologix will report a UADE to the FDA within 5 working days of becoming aware of the event, as required by regulations.

8.8.7. Adverse Event Definitions

The following event definitions will be applied during this study.

- *Death:* Any death occurring during the study period, regardless of cause.
 - *Aneurysm-related death* is defined as any death occurring within 30 days from the date of the procedure, regardless of cause, and death due to aneurysm rupture or following any procedure intended to treat the aneurysm.
 - *Cardiac-related death* is defined as death due to arrhythmia, heart failure (including cardiogenic shock), or myocardial infarction.
 - *Pulmonary-related death* is defined as death due to pulmonary edema, respiratory failure, or pulmonary embolism.
 - *Vascular-related death* is defined as death due to stroke, cerebral hemorrhage, or other clear vascular event that is not categorized as cardiac-related or pulmonary-related.
 - *Other* is to be used to identify a death due to any event that cannot be clearly categorized as above, but where some information is available.
 - *Unknown* is to be used to identify a death where no information is available.
- *Procedural Technical Failure* is defined as a failure of the Nellix system to be delivered and deployed, such that the procedure is not completed, or the device failure results in a serious complication, or a residual endoleak occurs that cannot be resolved during the index procedure and is still present at the 30 day CT as read by the Core Lab.
- *Major Adverse Event:* An event occurring during the study that meets one of the following criteria:
 - *All-Cause Death* (see above);
 - *Bowel Ischemia:* the lack of adequate blood flow to the intestines that requires intensification of medical therapy or surgical/endovascular intervention;

- *Myocardial Infarction*: the presence of raised levels of one or more cardiac biomarkers in comparison to local laboratory reference ranges;
- *Paraplegia*: Paralysis of the lower extremities inclusive of the lower trunk;
- *Renal Failure*: the need for temporary or permanent dialysis or $>0.5\text{mg/dL}$ increase in pre-operative serum creatinine level at two consecutive intervals;
- *Respiratory Failure*: pneumonia or respiratory failure requiring ventilator support beyond 24 hours post-procedure;
- *Stroke*: a sudden development of neurological deficit due to vascular lesions of the brain such as hemorrhage, embolism, or thrombosis that persists for >24 hours;
- *Procedural Blood Loss $>1,000\text{mL}$* : Estimated blood loss during the index procedure $\geq 1,000\text{mL}$.
- *Other Definitions*:
 - *Aneurysm Sac Enlargement*: Aneurysm sac diameter increase of $>5\text{mm}$ in late follow-up as compared to the initial post-operative measurement.
 - *Aneurysm Rupture*: bleeding or leaking of blood from the aneurysm subsequent to the index procedure.
 - *Clinically significant migration*: Core Lab reported stent distal movement $>10\text{mm}$ from the original implant location relative to the center of the distal renal artery resulting in an intervention or in a serious complication.
 - *Conversion to Open Repair*: open surgical repair of the abdominal aortic aneurysm due to unsuccessful delivery or deployment of the stent graft, due to complications or other clinical situations that precluded successful endovascular treatment, or at any time following initial successful endovascular treatment for any reason.
 - *Device Positional Stability*: Core Lab reported position of each stent relative to the center of the L3 vertebrae. Stable positioning is defined as within 5mm of the positioning on the first post-operative CT scan.
 - *Luminal Thrombus Requiring Intervention*: any endovascular surgical intervention after completion of the Nellix System implantation for resolution of endograft thrombosis.
 - *Distal Ischemia*: New onset of compromised peripheral blood flow resulting in femoral or peripheral arterial occlusion or stenosis (attributable to the index procedure and not related to natural progression of atherosclerotic disease) causing a threat to the viability of the limb and requiring surgical or percutaneous intervention; or stent graft occlusion requiring any intervention..
 - *Endoleak*: Clear evidence of contrast outside of one or both EndoBags which communicates with the aneurysm sac originating proximally at the infrarenal segment (Type IA), distally (Type IB); between components, if an extender is used (Type III); trans-device (Type IV); or from a patent collateral vessel (Type II: e.g., lumbar artery; inferior mesenteric artery). Contrast outside of an EndoBag that does not communicate with the aneurysm sac is not to be reported as an endoleak.

- *Migration*: Core Lab reported stent distal movement >5mm from the original implant location relative to the center of the distal renal artery.
- *Clinically significant migration*: Core Lab reported stent distal movement >10mm from the original implant location relative to the center of the distal renal artery resulting in an intervention or in a serious complication.
- *Occlusion*: Intervention for stent occlusion or as reported by the Core Lab.
- *Secondary procedure*: any non-diagnostic intervention after the index procedure intended to correct or repair an endoleak, device occlusion, migration, aneurysm sac expansion and/or a device defect (including infection).

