3. PROTOCOL SYNOPSIS

Title:	Prospective, Multicenter, Single Arm Safety and Effectiveness Study of Endo Vascular Abdominal Aortic Aneurysm Repair Using the Nellix® System with Continued Access
Short Title:	EVAS I Study with Continued Access
Study Devices:	Nellix EndoVascular Aneurysm Sealing System (Nellix System)
Study Sponsor:	Endologix, Inc.
Objectives:	To study the safety and effectiveness of the Nellix System for Endovascular Abdominal Aortic Aneurysm (AAA) repair. Procedures will be performed per the instructions for use, and per institutional protocols and standard of care for endovascular aneurysm repair. As such, this study will evaluate the safety and effectiveness of the device system among a wide range of physicians and in consecutively enrolled subjects to assess outcomes generalizability.
Study Design:	Prospective, multicenter, single arm study with consecutive, eligible subject enrollment at each site. All subjects will undergo the Endovascular Aneurysm repair procedure with the Nellix System. Sites have been chosen with a suitable research infrastructure and physician experience in endovascular aneurysm repair to ensure adequate enrollment. Subjects will be followed procedurally to discharge, at 30 days (primary safety endpoint), six months, one year (primary effectiveness endpoint) and annually thereafter to five years (total follow-up commitment).
Investigators:	Physicians (vascular surgeons or interventional cardiologists/radiologists as part of a multi-specialty team with vascular surgeons) at sites in the United States, and the European Union with well-established experience in open repair and endovascular aneurysm repair techniques (i.e., ≥ 25 cases in the prior year) may participate. Details of the procedural and device usage techniques are incorporated into the study protocol on the basis of prior experience with an earlier generation device system, and more recent device refinements that have been developed. In those cases where the investigator is an interventionalist, a vascular surgeon must be immediately available during the procedure to perform any necessary surgical intervention.
Subject Population:	Patients diagnosed with an abdominal aortic or aortoiliac aneurysm who are considered candidates for endovascular repair and who meet the study eligibility criteria may be screened for enrollment in the study.

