6.3. ADDITIONAL EVALUATIONS

Additional evaluations include:

- **Procedural and In-Hospital Evaluations:**
 - Volume of contrast media used;
 - Fluoroscopy time;
 - Total procedure time;[‡]
 - Time in ICU;[§]
 - Estimated blood loss;
 - % requiring blood transfusion;
 - Anesthesia time;[¶]
 - Time to hospital discharge;[£]
- **Mortality**, all-cause and aneurysm-related, within 30 days, at 6 months, and annually to 5 years;
- **MAE Individual Components** within 30 days, at 6 months, and annually to 5 years;
- **Composite MAEs** after 30 days, at 6 months, and annually to 5 years;
- **Aneurysm Rupture** within 30 days, at 6 months, and annually to 5 years;
- **Conversion to Open Surgical Repair** within 30 days, at 6 months, and annually to 5 years;
- **Adverse Events** (serious and non-serious) within 30 days, at 6 months, and annually to 5 years;
- **Device Performance** (aneurysm sac diameter change from the first post-operative visit; device migration; clinically significant device migration, incidence of endoleak) at 30 days, 6 months, and annually to 5 years;
- **Renal Function** pre-discharge and at 30 days, 6 months, and annually to 5 years, as assessed by the estimated glomerular filtration rate (eGFR) and changes over time;
- **Device Patency and Integrity** within 30 days, at 6 months, and annually to 5 years, as determined by contrast-enhanced CT scan, and as assessed by the independent core laboratory, inclusive of:
 - Patent luminal flow
 - Absence of kinking or occlusion
 - Absence of stent fracture
 - Absence of device failure
- **Luminal Thrombus Requiring Intervention** within 30 days, at 6 months, and annually to 5 years;
- **Secondary Procedure** within 30 days, at 6 months, and annually to 5 years for resolution of endoleak, device occlusion, migration, aneurysm sac expansion and/or a device defect.

[‡]Elapsed time from the first break of skin to final closure (i.e., skin to skin time).

[¶]Elapsed time from the initiation to the end of the anesthesia protocol.

[§]Elapsed time from the first administration of anesthesia to release from the ICU or post-anesthesia care unit providing ICU-level care. If the patient is not admitted to the ICU, this is defined as 0 hours.

[£]Elapsed time from initiation of the procedure to physical discharge from the hospital.

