8.5.4. Subject Enrollment

Enrollment in the study only occurs upon advancement of the study device into the subject's vasculature. Therefore, the date of study enrollment is the date of the Nellix System implant, as documented in the Visit Date field in the Index Procedure eCRF. If the device does not contact the patient, the patient will be considered as screen failure and the assigned study number will not be given to another patient. If, during the index procedure, the device is introduced but is not implanted and/or there is conversion to open surgery, the patient will be followed until the 30 day follow-up.

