10.8 ADDITIONAL EVALUATIONS

- *Procedural and In-Hospital Evaluations:* The estimated blood loss volume, % of subjects receiving a blood transfusion, contrast volume, fluoroscopy time, endovascular device time, Polymer volume used, procedure time, anesthesia time and type, frequency of concomitant procedures, ICU time, time to hospital discharge, and % of subjects discharged to skilled nursing facilities or assisted living facilities who were not prior residents will be presented descriptively. Qualitative variables will be presented with rate. Quantitative variables will be presented with mean, standard deviation, median, minimum and maximum.
- *Mortality:* The proportion of subjects with mortality (all-cause and aneurysm-related) will be presented at 30 days and at each subsequent time point for which data are available (i.e., six months, and annually at years 1 through 5). A descriptive analysis and a Kaplan-Meier analysis of all-cause and aneurysm-related mortality through 30 days and for late follow-up including 30 days will be presented.
- *Major Adverse Events (MAE) Individual Components:* The proportion of subjects experiencing each category of MAE within 30 days and after 30 days at each subsequent time point for which data are available will be presented.
- *Composite Late MAEs (after 30 days):* The proportion of subjects experiencing an MAE after 30 days will be presented at each subsequent time point for which data are available. A descriptive analysis and a Kaplan-Meier analysis of the MAE composite will be

presented for follow-up through 30 days and for late follow-up including 30 days. The descriptive analysis will present the rates for the composite MAE and each individual adverse event that is part of the composite.

- *Aneurysm Rupture*: The proportion of subjects experiencing a rupture of the aneurysm will be presented at 30 days and at each subsequent time point for which data are available.
- *Conversion to Open Repair*: The proportion of subjects undergoing surgical conversion to open repair will be presented at 30 days and at each subsequent time point for which data are available.
- *Serious Adverse Events (SAEs)*: The proportion of subjects experiencing an SAE will be presented descriptively by time point.
- *Non-serious AEs*: The proportion of subjects experiencing a non-serious AE will be presented descriptively by time point.

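### The last limb of aneurysm-related death has no time window, causal test or stated exclusion of the index implant, so late aneurysm-related mortality is not well defined

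*Combined protocol and SAP*

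**What the plan says.** Section 8.8.7 first defines death in general: "Any death occurring during the study period, regardless of cause". It then defines aneurysm-related death through three limbs. The first is "any death occurring within 30 days from the date of the procedure, regardless of cause". The second and third come together: "death due to aneurysm rupture or following any procedure intended to treat the aneurysm".

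The same section separately defines a secondary procedure as a non-diagnostic intervention performed after the index procedure for a listed set of device problems. The death definition does not use that term.

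Section 6.3 lists mortality as two measures, "all-cause and aneurysm-related, within 30 days, at 6 months, and annually to 5 years". Section 10.8 adds proportions at each time point and the following: "A descriptive analysis and a Kaplan-Meier analysis of all-cause and aneurysm-related mortality through 30 days and for late follow-up including 30 days will be presented". Section 11.2 (item 5) has the CEC categorize events by the definitions in the protocol.

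**The concern.** The first limb is bounded in time and the second is bounded by cause. The third is bounded by neither: *following* states only an order of events. It also does not say whether the procedure in question is the index implant, a re-intervention, or either.

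The purpose of reporting aneurysm-related mortality beside all-cause mortality is to separate deaths that bear on the device or the disease from the background mortality of the population. If the third limb admits deaths by sequence alone, the late part of the measure depends on who had a re-intervention as well as on why people died.

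That matters in this trial. Section 8.6 records a report to the regulator of migration, Type IA endoleak and sac enlargement above expectation at two years, and then sets out secondary interventions for them. Late device-related mortality is therefore a question readers will bring to the five-year results.

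**Working it through.** The documents give no rate, sample size or alpha for aneurysm-related death, so there is no figure to reproduce. The check is on logic.

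**Inputs**

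- Every subject is treated: "All subjects will undergo the Endovascular Aneurysm repair procedure with the Nellix System" (section 3).
- Nobody is enrolled before the procedure has begun: "Enrollment in the study only occurs upon advancement of the study device" (section 8.5.4).
- The three limbs are those of section 8.8.7. No other section adds a window, a causal test or an exclusion of the index implant to the third limb.

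**Literal reading.** Let D be all deaths in enrolled subjects, A the deaths on days 0 to 30, and C the deaths after any procedure aimed at the aneurysm. All deaths up to day 30 are in A. Every later death comes after the index repair, so it is in C. Hence A ∪ C = D: aneurysm-related deaths divided by all deaths is 1.0 at every time point, and the two Kaplan-Meier curves coincide.

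**Narrower reading.** Restrict the third limb to procedures after the index implant. The constructed cases below compare the readings with the definition proposed under the fix.

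| Death | Literal | Re-intervention only | Proposed |
|---|---|---|---|
| Day 20, any cause | Yes | Yes | Yes |
| Year 2, rupture | Yes | Yes | Yes |
| Year 4, unrelated cause, no re-intervention | Yes | No | No |
| Year 4, unrelated cause, re-intervention in year 1 | Yes | **Yes** | No |
| Year 3, implant infection, no rupture or re-intervention | Yes | **No** | Yes |

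The two cells in bold are the defect that survives the sensible reading. One death is counted because of sequence alone. The other is caused by the device and is missed, although section 8.8.5 lists implant infection and erosion among the anticipated events.

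**Other readings.** The third limb could also be meant to carry a window after each procedure, or an implied causal link. Either would remove the first bold cell. A window alone would not rescue the second. A causal link would do so only if the index implant counted as a qualifying procedure. The documents do not choose among these readings.

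**Reach.** Primary safety (sections 6.1 and 10.6) uses all-cause death within the 30-day composite. Treatment Success (sections 6.2 and 10.7) does not use aneurysm-related death. Up to day 30 the first limb already captures every death, so the ambiguity cannot change the 30-day figure. What remains is the aneurysm-related proportions and curves after day 30, out to five years.

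**The case against.** A reader might infer that the measure simply equals all-cause mortality. The documents do not support that as the intended meaning or the likely result. It would make the 30-day and rupture limbs redundant and leave the separate reporting in sections 3, 6.3 and 10.8 without purpose. The definition also contrasts *the* procedure in its first limb with *any* procedure in its last, which points to the index procedure against later ones. Nothing suggests that a physician committee would label every death aneurysm-related. This part of the objection stands: the literal result shows that the wording is loose and does not predict what will be reported.

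It can also be said that little is lost. The measure is descriptive and all-cause mortality appears beside it. Section 8.8.7 sorts deaths into cardiac, pulmonary, vascular, other and unknown. Section 8.8.1 has the investigator judge each event's relationship to device or procedure, and section 8.8.2 requires death certificates. This stands as a limit on consequence. The raw information exists, and one summary label is at fault. It does not settle how that label is to be assigned, because the committee is told to follow the written definition.

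A further argument is that any error is over-inclusive and so counts against the device. That holds for the literal reading only. On the re-intervention reading, missing a late device-caused death works in the device's favor.

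Finally, narrowing a mortality definition after data have been seen can favor the sponsor. Relative to the literal reading, a narrower definition can only keep or lower the count. This objection is sound and shapes the fix.

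**Conclusion.** The point holds in limited form. The third limb lacks a window, a causal test and a stated scope, and no other part of the plan supplies them. Even on the sensible reading it counts unrelated deaths that come long after a re-intervention and gives no place to a late device-caused death without rupture or re-intervention.

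The effect is confined to descriptive aneurysm-related mortality after 30 days and up to five years. The primary endpoints, alpha, power and sample size do not change.

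The number of deaths affected cannot be derived from the documents, which give neither late mortality nor the frequency of secondary procedures among those who die. Even a count of deaths after re-intervention would overstate misclassification, since some of those deaths would be truly aneurysm-related. The conclusion rests on the wording alone and needs no assumed rate. The definition should be corrected, but it does not threaten the trial's main conclusions.

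**What to change.** Redefine aneurysm-related death in section 8.8.7 as either of:

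- death from any cause within 30 days of the index procedure, or of any secondary procedure for the aneurysm or the device; or
- death at any time that the CEC adjudicates as caused by aneurysm rupture, the device, or an aneurysm procedure.

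Apply this to all deaths, including those already recorded. Any change now comes after the two-year data described in section 8.6 were reviewed. The sponsor should therefore disclose it as post hoc and report the late proportions and Kaplan-Meier curves twice: under the current wording as the CEC has applied it, stating which reading that was, and under the revised wording.

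The cost is a small amount of re-adjudication and a definition change that must be declared. No new data collection is needed. All-cause death during the study is already a major adverse event, section 11.2 sends those events to the CEC, and section 8.8.2 already calls for death certificates, discharge summaries for hospitalized patients and other source documents as available.

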6.2. PRIMARY EFFECTIVENESS

The primary effectiveness endpoint is defined as the rate of Treatment Success at one year. Treatment Success is a composite of outcomes clinically relevant to the endovascular repair of infrarenal AAA as follows. Event and related definitions are provided in [§8.8.7](#).

Treatment Success: Procedural technical success [¶] and absence of:

- Abdominal aortic aneurysm rupture;
- Conversion to open surgical repair;
- Endoleak Type I or III at 12 months;
- Clinically significant migration[‡];
- Aneurysm enlargement; or
- Secondary endovascular procedure up to 12 months for resolution of
 - Endoleak (Type I or Type III)
 - Device obstruction or occlusion
 - Device migration
 - Abdominal aneurysm sac expansion
 - Device defect[‡]

Refer to §10.7 for primary effectiveness endpoint analysis details.

[¶] Procedural technical success is deployment of the Nellix System in the planned location and without unintentional coverage of both internal iliac arteries or any visceral aortic branches and with the removal of the delivery system.

[‡]Refer to protocol [§8.8.1](#) for detailed definitions.

Confidential. This document and the information contained herein may not be reproduced, used or disclosed without written permission from Endologix, Inc.

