10.3 GENERAL NOTES

Analyses of MAEs and other adverse events will be conducted at exact time points. Early events are defined as those occurring from the date of the procedure to 30 calendar days post-operatively. Late events are defined as those occurring from after 30 calendar days post-operatively (from day 31 forward). Events within six months and one year, respectively, are those occurring up to and including

*Steele R and Torrie J. Principles and Procedures of Statistics. 1960. McGraw-Hill, New York.

Confidential. This document and the information contained herein may not be reproduced, used or disclosed without written permission from Endologix, Inc.

180 days and 365 days following the procedure.

For categorical variables, summary statistics will include counts and proportions. Confidence limits for proportions will generally be given; for binary variables the confidence limits will be computed using the exact binomial distribution. Supportive multivariate analyses of stratified comparisons of categorical variables will be performed using appropriate logistic or Cox regression.

For continuous variables, summary statistics will include means, standard deviations, medians, and range. Groups will be compared using *t*-tests or analysis of variance, or Kruskal-Wallis tests will be used to compare more than two groups (such as trial sites). When multiple comparisons are performed after ANOVA, Scheffé's method will be used. The exact Wilcoxon test will be used to compare continuous variables where severe departures from normality are observed.

For ordinal variables, comparisons will be performed using the exact Wilcoxon rank-sum test. Unless otherwise specified, the exact form of each algorithm will be the default of SAS Version 9.1 or later. Some preliminary descriptive analyses may be done with other software tools to be specified.

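### The rupture definition starts after the index procedure, so a rupture during implantation that is sealed endovascularly can be scored as Treatment Success (a small classification gap that favours the device)

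*Combined protocol and SAP*

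**What the plan says.** Section 6.2 lists "Abdominal aortic aneurysm rupture" first among the events that must be absent for Treatment Success, and refers the reader onward: "Event and related definitions are provided in" section 8.8.7. That section defines rupture as "bleeding or leaking of blood from the aneurysm subsequent to the index procedure". No other section widens the window. Under section 11.2 the Clinical Events Committee categorizes events by the definitions in the protocol, so this wording governs.

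Treatment Success also requires procedural technical success. The section 6.2 footnote describes this as "deployment of the Nellix System in the planned location and without unintentional coverage of both internal iliac arteries or any visceral aortic branches", with the delivery system removed. Section 8.8.7 separately defines Procedural Technical Failure. It covers a procedure that is not completed, a case where "the device failure results in a serious complication", or a residual endoleak still seen at the 30-day CT.

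Section 10.3 sets the time bins for analysis: "Early events are defined as those occurring from the date of the procedure to 30 calendar days post-operatively". Section 8.8.5 lists both aneurysm rupture and "Arterial damage or trauma (e.g., bleeding, perforation, dissection, rupture)" among the anticipated adverse events.

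**The concern.** Exclusion criterion 6 bars ruptured and leaking aneurysms, so a rupture in the procedure room is a new event. The time limit is therefore not needed to screen out pre-existing ruptures. Its literal effect is to leave out the procedure itself, although other parts of the composite (technical success, conversion for failed delivery or deployment) do cover it.

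At stake are the classification of such a subject in the primary effectiveness endpoint and the completeness of the rupture rates in section 10.8. Any misclassification runs one way: a failure is counted as a success.

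**Working it through.** **Tracing the case.** Take a rupture during implantation that is sealed endovascularly, with the implant completed as planned.

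- *Rupture (8.8.7):* not met unless bleeding continues or recurs after the procedure.
- *Conversion to open repair (8.8.7):* this includes conversion "due to complications or other clinical situations that precluded successful endovascular treatment", but here there is no open repair.
- *Secondary procedure (8.8.7):* must follow the index procedure, and rupture is not among the listed reasons. Sealing on the table does not count.
- *Technical success (6.2 footnote):* position, branch coverage and delivery-system removal can all be satisfactory despite the rupture.
- *Technical failure (8.8.7):* met only if a device failure led to a serious complication or an endoleak persisted at the 30-day CT. A rupture without device failure passes. A rupture from device failure with a serious complication is a technical failure here, yet still satisfies the 6.2 footnote, so the two definitions disagree on that case.
- *Endoleak at 12 months, clinically significant migration, enlargement:* not implied by a sealed rupture.
- *Safety (6.1):* rupture is not a listed MAE. It registers only through a component such as death, blood loss of at least 1,000 mL, or myocardial infarction.

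Such a subject can therefore be a Treatment Success with no MAE.

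**Size.** Inputs from sections 10.7.1 and 10.7.2: n = 132 at one year, null rate 0.80, assumed rate 0.88, one-sided alpha 0.05, drop-out 12%. The plan's recruitment figure reproduces: 132/0.88 = 150. The test uses the tail sum

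P(X ≥ x) = Σ C(132,k) · 0.80^k · 0.20^(132−k), for k from x to 132.

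- x = 114: p = 0.0383, reject.
- x = 113: p = 0.0625, do not reject.

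The critical count is thus 114. Exact power at 0.88 is 76.7%, against the stated 80%; that difference is separate from this point.

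Let q be the proportion of subjects with an intra-procedural rupture that escapes every other component. The documents do not give q, so the range is assumed. Suppose the success rate with these cases counted as failures is exactly 0.80; the scored rate is then 0.80 + q. The chance of at least one case is 1 − (1 − q)^132, and the rejection probability is P(X ≥ 114) at 0.80 + q.

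| q (assumed) | expected cases, 132q | chance of at least one | rejection probability |
|---|---|---|---|
| 0 | 0 | 0 | 3.8% |
| 0.25% | 0.33 | 28% | 4.5% |
| 0.5% | 0.66 | 48% | 5.1% |
| 1% | 1.32 | 73.5% | 6.8% |
| 2% | 2.64 | 93% | 11.4% |

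The lower rows would need a high rate: q counts only ruptures that pass every other test, so it cannot exceed the total rate of intra-procedural rupture and is probably well below it.

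**The case against.** The strongest reply is that the case is narrow. The subject must rupture, be sealed without conversion, have the implant completed as planned, and have no device failure with a serious complication, no persisting endoleak and no later bleeding. To escape the safety endpoint too, the subject must have no MAE, and the myocardial infarction definition asks only for a raised biomarker. This stands and limits the weight of the point.

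It can also be argued that Treatment Success is about durable exclusion, so a complication contained on the table belongs with the adverse events. That is defensible as a choice, but the plan does not state it, and the composite already includes procedural failures.

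Three stronger readings are not supported:

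- A reader might infer that section 10.3 contradicts the definition. It does not. It sets time bins; it does not define events. A rupture hours after the procedure is an early event under both sections.
- A reader might infer that the event goes unrecorded. It would be reportable as an anticipated adverse event if clinically significant (8.8.5), would fall within the adverse event summaries (10.8), and all AEs and SAEs receive an independent safety review (11.2). The gap is in endpoint classification only.
- A reader might infer that up to 2% of subjects, or 3 of 150, would be misclassified and that one of them could decide the trial. The 2% is an assumption, and only the subset that escapes every other component matters. The one-subject boundary between 113 and 114 applies equally to every component of the composite.

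**Conclusion.** The gap is real but minor. As written, a new rupture during implantation can be scored as Treatment Success if no other component catches it, and it can be absent from the rupture rates in section 10.8. The documents do not support saying that every such rupture would be missed: those followed by bleeding, those leading to conversion, and those from device failure with a serious complication are caught, the last under the 8.8.7 failure definition but not under the 6.2 footnote.

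The size cannot be fixed from the documents. If the escaping subset were 0.5% or less, the exact test's rejection probability at the boundary would rise from 3.8% to at most 5.1%, close to the nominal 5%. The conclusion rests on reading the time limit literally, as excluding the procedure itself, and on the definitions being applied as written.

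**What to change.** In section 8.8.7, extend the rupture definition to bleeding or leaking from the aneurysm *during or* after the index procedure, and apply it to the section 6.2 composite and the section 10.8 rupture evaluation. Reconcile the technical success footnote in 6.2 with the Procedural Technical Failure definition in 8.8.7, so that one is the complement of the other.

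Timing matters. Section 8.6 refers to two-year data reported in October 2016, so one-year outcomes may already be known and a changed endpoint could look data-driven. The report should therefore list any intra-procedural ruptures and give the primary effectiveness test under both the current and the widened definition. If there are none, one sentence closes the matter.

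The cost is a few words, a check of index-procedure events, and possibly a slightly lower success rate. If the assumed 88% counts such cases as successes, rescoring them gives 0.88 × (1 − q): exact power at n = 132 falls from 76.7% to 74.2% for q = 0.25% and to 71.6% for q = 0.5%.
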